4.1.5 Subgroup analyses for efficacy

Subgroups are defined based on the following categorizing factors:

- Gender (Male, Female)
- Age (18 -< 65, 65 -<75, >=75 years)
- Weight at screening (<50, 50-<75, 75 -< 100, 100 -<125, >= 125 kg)
- BMI at screening (Underweight: < 18.5 kg/m², Normal weight: 18.5 -< 25 kg/m², Overweight: 25 -< 30 kg/m², Obese: >= 30 kg/m²)
- Race (Asian, Black or African American, White, Other)
- Baseline eGFR (Normal: >= 90 mL/min/1.73m², Mildly impaired: 60 -<90 mL/min/1.73m², Moderately impaired: 30 -< 60 mL/min/1.73m², Severely impaired: <30 mL/min/1.73m²)
- Disease type (PV/PF) and PV subtype (mucosal-dominant vs (muco-)cutaneous)
- Disease status (relapsing vs newly diagnosed)
- Disease severity (PDAI activity score <30 and PDAI activity score ≥30); moderate (15≤PDAI ≤44) vs severe (PDAI ≥45)
- Region (North America; Europe; Asia; Rest of World)

Subgroup analyses will be performed on the primary and key secondary efficacy endpoints on the mITT population.

Following table summarizes the analyses:

Table 5: Summary of analyses

Endpoint	PV	PF ^f	All (PV+PF)	Strategy
Proportion CRmin	X ^{1,c,p}	X	X ^{2,c,p,s}	C+T
NCPD	X ^{2,c,p}	X	X ^{2,s}	H+T
Time to CR	X ^{2,c,p}	X	X ^{2,s}	C+T
Time to DC	X ^{2, c,p}	X	X ^{2,s}	C+T
Time to CRmin	X	X	X	C
Proportion DC / CR	X	X	X	C
Proportion treatment failure	X		X	T
Number of flares (incidence rate)	X		X	T
Proportion of participants with flare	X		X	T
Time to first flare	X		X	T
Duration of CRmin	X	X	X	T
PDAI, QoL, C-GTI	X		X	T
¹ Primary endpoint ² Key secondary endpoint ^c Besides main analysis also supplementary analysis will be performed. ^f PF as part of subgroup analysis or as separate analysis. ^p Also analysis on PP analysis set and mITT excluding data impacted by the conflict in Ukraine will be performed. ^s Also subgroup analyses will be performed. C=composite strategy (taking into account ICEs) H=hypothetical strategy (taking into account ICEs) T=treatment policy strategy (ignoring ICEs)				

4.2 PHARMACOKINETICS

4.2.1 Available data

Blood samples will be collected for the determination of efgartigimod concentration at the time points indicated in the schedule of assessments (see section 9.5). Sampling will be done predose on IMP administration visits (within 2 hours before IMP).

An additional PK sample will be taken on day 3 and on day 11 (±1 day) until samples from 24 participants are obtained.

	
Statistical Analysis Plan
	

ARGX-113-1904
	
Final analysis
	
Final 2.0 of 22NOV2023

PK data obtained during off treatment period from participants who achieved CRmin (ie, no longer receiving weekly administrations of IMP) will not be included in the descriptive statistics.

In addition, following PK samples will be excluded from the descriptive statistics based on time since previous IMP:

- When PK samples are taken outside the visit windows. The study visit windows are ± 2 days, i.e. if PK sample is not within last IMP+7 days ± 2 days. On Day 3 and Day 11 the visit window is ± 1 day (ie, ± 24 h).
- When a predose sample is taken after IMP administration.
- When the IMP administration prior to the scheduled PK sample is missed (not applicable for Day 1).

A remark with reason for exclusion of the timepoint will be added in the appropriate listing.

4.2.2 Derivation rules

PK concentrations will be reported in ng/mL by the lab and will be converted to ug/mL for analyses.

4.2.3 Presentation of results

Individual concentration data and actual blood sampling times from dose administration for PK assessments will be listed.

Descriptive statistics per time point on concentration data will be presented in tables.

4.3 PHARMACODYNAMICS

4.3.1 Available data

The following pharmacodynamic markers will be measured in serum: total immunoglobulin G (IgG), IgG subtypes (IgG1, IgG2, IgG3, and IgG4) and anti-Dsg-1/ Dsg-3 antibodies.

4.3.2 Derivation rules

Changes and percent changes vs baseline will be calculated. Participants with a baseline value below the limit of quantification (BLQ) will be excluded when computing the change from baseline and the percent change from baseline. Values of anti-Dsg-1/Dsg-3 above or below limit of quantification will be imputed by the upper or lower limit of quantification respectively. This will be explained by a footnote in the appropriate tables. Limits of quantification are provided by the lab. For total IgG and IgG subtypes, no imputation will be applied. Listings will always show the non-imputed values.

In addition, for all pharmacodynamic endpoints, descriptive statistics of the actual vales will also include GM and GSD. GM and GSD are not applicable for descriptive statistics of the absolute changes from baseline. For these selected endpoints, descriptive statistics of percent changes from baseline will also include GM and GSD. GM and GSD of percent changes from baseline are calculated as $100 \times \{ \exp(\theta) - 1 \}$

	Statistical Analysis Plan	
ARGX-113-1904	Final analysis	Final 2.0 of 22NOV2023

where θ is respectively the arithmetic mean and arithmetic SD of a variable calculated as $\log(\text{aval}) - \log(\text{base})$.

4.3.3 *Presentation of results*

All pharmacodynamic endpoints will be summarized by means of descriptive statistics at each analysis visit. Actual values, changes from baseline and percent changes from baseline will be tabulated. Also, the same subgroup analyses will be performed as for efficacy.

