of the skin surface. PF diagnosis follows the investigational tools that are used in PV. At histology, a cleft in the subcorneal or the superficial granular layer can be seen. DIF shows the intercellular deposition of IgG within the epidermis, and the IIF reveals the presence of serum autoantibodies against intercellular components of the skin. ELISA tests quantify the positive level of anti-Dsg-1 antibodies in serum, whereas the search for anti-Dsg-3 antibodies is negative.

Like PV, PF does not tend to amend spontaneously. Treatment is always needed, with the aim at healing existing lesions and preventing the appearance of new lesions as soon as possible.

Basic and clinical research has led to a better understanding of the mechanisms of pemphigus diseases and novel therapies have been developed. Nonetheless, long diagnostic delay and suboptimal treatment are important concerns in pemphigus diseases. As described above, a drug with a faster onset of action is needed so that quicker DC can be achieved in combination with low starting doses of corticosteroids (eg, prednisone at 0.5 mg/kg per day), and CR can be attained and maintained while the patient reaches rapidly minimal corticosteroid dose (prednisone ≤ 10 mg/day) or even no concomitant treatment (off prednisone therapy).

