2. GENERAL METHODOLOGY

2.1 ANALYSIS SETS

2.1.1 *Analysis sets*

The following analysis sets will be considered in the statistical analysis:

All screened participants set (SCR):	participants who signed an informed consent to participate in the study
Modified Intent-to-treat analysis set (mITT):	all participants who were randomized into the study and received at least one dose, or part of a dose, of IMP
Per Protocol set (PP):	all participants in the mITT population for whom no major protocol deviations affecting the efficacy and data validity were reported
Safety analysis set (SAF):	all participants who were randomized into the study and received at least one dose, or part of a dose, of IMP
PK analysis set (PK)	all participants in the safety analysis set for whom at least one post-baseline serum PK concentration is available
PD analysis set (PD)	all participants in the safety analysis set for whom at least one post-baseline serum PD concentration is available

Note: Having signed an informed consent is defined as having a complete informed consent signature date in the database.

The efficacy analyses will be done on the mITT analysis set. The analyses of primary and key secondary efficacy endpoints will be repeated on the PP analysis set. The general characteristics and safety analyses will be done on the safety analysis set. PK analysis will be performed on the PK analysis set. PD analysis will be done on the PD analysis set. Immunogenicity will be analyzed on the safety analysis set.

2.1.2 *As planned versus as actual analysis*

All analyses on the mITT and PP analysis set will be performed according to the planned randomization group. All other analyses will be performed according to the actual received IMP.

	Statistical Analysis Plan	
ARGX-113-1904	Final analysis	Final 2.0 of 22NOV2023

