2.3.3 Values below or above a threshold

Safety values expressed as below (or above) the detection limit will be imputed by the value of the detection limit itself. Listings will always show the non-imputed values.

Total IgG and IgG subtype values expressed as below or above the limit of quantification (BLQ or ALQ, respectively) will not be imputed. For anti-Dsg-1/Dsg-3, BLQ and ALQ values will be imputed by the value of the detection limit itself. Listings will always show the non-imputed values.

PK concentrations BLQ will be flagged as such in the listings. For descriptive statistical analysis, all BLQ values will be set to zero. For ALQ values, all ALQ values will be set to the upper limit of quantification for descriptive analysis. Listings will always present the original value.

Anti-drug antibodies (ADA) against efgartigimod: titer of positive ADA samples reported as ‘negative titer’ will be imputed by 1.

Antibodies (Ab) against rHuPH20: titer of positive rHuPH20 Ab samples reported as ‘negative titer’ will be imputed by 5.

Neutralizing antibodies (NAb) against rHuPH20: titer of positive rHuPH20 NAb samples reported as ‘negative titer’ will be imputed by 100.

Listings will always present ‘negative titer’.

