3.2 DEMOGRAPHIC AND OTHER BASELINE CHARACTERISTICS

3.2.1 *Available data*

The following parameters will be available:

- Demographics: sex at birth, age at informed consent, race and ethnicity (if collection permitted), region, childbearing potential, height, weight and BMI at screening, year of birth, date of signing ICF (listed only).

	
Statistical Analysis Plan
	

ARGX-113-1904
	
Final analysis
	
Final 2.0 of 22NOV2023

- Baseline disease characteristics: date of pemphigus onset (listed only), date of pemphigus diagnosis, pemphigus type (vulgaris/foliaceus) and subtype (mucosal-dominant / mucocutaneous / cutaneous), type of procedure used for confirmation of diagnosis (cutaneous histology / direct immunofluorescence / indirect immunofluorescence / ELISA), relapsing (yes / no), newly diagnosed (yes / no), number of relapses (if applicable), prior use of immunosuppressants (yes / no), prior use of rituximab (yes / no), PDAI activity score and PDAI total score at baseline, baseline severity [PDAI activity <30/≥30 as well as PDAI activity score 15-44 (moderate), ≥45 (severe)], ABQOL total score at baseline, Karnofsky performance score, positive (≥ 20 RU/ml) anti-Dsg antibodies (aDsg1 only, aDsg3 only, both aDsg1 and aDsg3, neither aDsg1 nor aDsg3), prednisone equivalent dose per body weight at baseline (mg/kg/day), prednisone equivalent dose at baseline (mg/day) and stratification factors (as randomized).

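### SAP 4.3.2 drops anti-Dsg baselines below quantification but keeps those above it at the upper limit, which understates the within-arm percent reduction for those participants; add a companion summary

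*SAP*

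**What the plan says.** SAP 4.3.2 (pharmacodynamics, derivation rules) treats the two ends of the assay range differently at baseline.

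- Low end: "Participants with a baseline value below the limit of quantification (BLQ) will be excluded when computing the change from baseline". The same exclusion covers percent change.
- Both ends, anti-Dsg only: "Values of anti-Dsg-1/Dsg-3 above or below limit of quantification will be imputed by the upper or lower limit of quantification respectively". No exclusion, separate summary or sensitivity analysis is given for a baseline above the upper limit. Total IgG and its subtypes are not imputed.
- SAP 2.3.3 gives the same imputation in different terms: "For anti-Dsg-1/Dsg-3, BLQ and ALQ values will be imputed by the value of the detection limit itself". One section speaks of a detection limit and the other of a limit of quantification.
- No limit is stated: "Limits of quantification are provided by the lab".

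On serostatus, SAP 3.2.1 defines groups by "positive (≥ 20 RU/ml) anti-Dsg antibodies (aDsg1 only, aDsg3 only, both aDsg1 and aDsg3, neither aDsg1 nor aDsg3", but uses them only to describe the population at baseline. The PD set carries no serostatus condition: "all participants in the safety analysis set for whom at least one post-baseline serum PD concentration is available". Protocol 5.1 (criterion 3) accepts indirect immunofluorescence and/or ELISA, so ELISA-negative participants can enrol. For pemphigus foliaceus (PF), Protocol 2.2 says that ELISA finds anti-Dsg-1, "whereas the search for anti-Dsg-3 antibodies is negative".

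The results appear in Tables 14.2.3.3 (overall) and 14.2.3.4 (by the efficacy subgroups of SAP 4.1.5, which include disease type and PV subtype but not serostatus).

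**The concern.** A percent change needs a usable denominator. The SAP accepts this at the low end and not at the high end. A baseline recorded at the upper limit is smaller than the true value, so a fall from it looks smaller than it was. If the follow-up value is also above the limit, the recorded change is zero whatever happened.

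The serostatus gap is a separate matter. A participant negative for an antigen has no target antibody to lower. Under the SAP, whether that participant is counted depends only on whether the background reading clears the lower limit, which has nothing to do with the question the table should answer.

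Anti-Dsg-1 and -3 serum levels are a listed secondary PD endpoint (Protocol 3), and Protocol 2.3.2 links their fall to clinical improvement in phase 2. What is at stake is how accurately the trial describes the drug's mechanism. No test result depends on it.

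**Working it through.** The plan states no figure on this point, so there is none to reproduce. The numbers below illustrate the stated rule on assumed inputs.

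**Inputs from the documents:** the rules above; the 20 RU/ml cut (SAP 3.2.1); up to about 30 PF participants among about 213 (SAP 1.3).

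**Assumptions:** a true fall of 65% on drug (Protocol 2.3.2 gives this as the maximum mean fall in total IgG in immune thrombocytopenia, not anti-Dsg in pemphigus) and 20% on placebo; ALQ shares up to 30%; baselines 1.25 to 3 times the upper limit.

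**1. One participant.** With a true baseline of k times the upper limit (k > 1) and true fall r, the shown reduction is 1 − min(1, k(1 − r)).

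| k | r = 65% | r = 20% |
|---|---|---|
| 1.25 | 1 − 0.4375 = 56.25% | 1 − 1.00 = 0% |
| 1.5 | 1 − 0.525 = 47.5% | 0% |
| 2 | 1 − 0.70 = 30% | 0% |
| 3 | 1.05, capped at 1: 0% | 0% |

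**2. Drug-arm mean,** with a share s of ALQ baselines and everyone else showing 65%: s × (step 1 value) + (1 − s) × 65%.

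- s = 10%: 4.75 + 58.5 = 63.25% at k = 1.5; 3 + 58.5 = 61.5% at k = 2; 58.5% at k = 3.
- s = 30%: 14.25 + 45.5 = 59.75% at k = 1.5; 9 + 45.5 = 54.5% at k = 2; 45.5% at k = 3.

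Leaving out ALQ baselines returns 65% in this constant-fall example.

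**3. Geometric mean.** The SAP's geometric percent change averages log(value) − log(baseline), so it inherits the bias. For s = 30%, k = 2: 0.7 × ln 0.35 + 0.3 × ln 0.70 = −0.735 − 0.107 = −0.842, and 1 − exp(−0.842) = 56.9% instead of 65%.

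**4. Drug minus placebo.** The true gap is 65 − 20 = 45 points. With s = 30% in both arms, placebo shows 0.7 × 20 = 14%. The gap is 59.75 − 14 = 45.75 points at k = 1.5, 54.5 − 14 = 40.5 at k = 2, and 45.5 − 14 = 31.5 at k = 3. It can therefore rise slightly or shrink.

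**5. The BLQ exclusion works the other way.** A BLQ baseline kept at the lower limit would show 0% if the titre falls. With 20% of such participants kept, the mean would be 0.8 × 65 = 52%; dropping them leaves 65%.

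**6. Quantifiable seronegatives.** 30/213 = 14% is the most that PF can add to the pooled anti-Dsg-3 table, reached only if every PF participant reads above the lower limit. If all did and everyone else fell 65%, the mean would be:

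- background does not fall: 0.86 × 65 = 55.9%
- background falls 30%: 55.9 + 0.14 × 30 = 60.1%
- background falls 65% and stays above the lower limit: 65%, so no dilution.

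Antigen-negative PV participants would add to this by an amount the documents do not give.

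**The case against.** The strongest reply is that the distortion may not occur. It needs baselines that are actually reported as ALQ. If the laboratory dilutes and re-assays high samples, the first part of the point disappears, and the documents do not say whether it does. This stands, and it is why no overall size can be claimed.

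Several other points also stand.

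- The planned output includes medians and quartiles (SAP 2.4.1), which resist the distortion better. In a simulation with 14% seronegatives whose background does not change (assumed seropositive median 150 RU/ml, geometric SD 2.5; seronegative median 5; lower limit 2), the mean change is about −55%, −52% and −45% with no upper limit, 12% ALQ and 32% ALQ. The median is −63.3%, −61.8% and −57.3%.
- The disease-type subgroup tables remove the PF contribution from the PV result, though they do not separate antigen-negative PV participants.
- Imputation is footnoted and the listings show unimputed values. That discloses the problem but provides no corrected summary.
- Protocol 8.9.1 describes the drug as lowering IgG of all subtypes, so an IgG background signal may fall too.
- The tables are descriptive, and no PD endpoint is in the testing sequence (SAP 4.1.4).
- Replacing the main table would be debatable. Excluding ALQ baselines removes the highest titres, and selecting on a baseline cut invites regression to the mean.

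None of this answers the narrower point: for a baseline reported as ALQ, the rule as written understates a fall.

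**Conclusion.** The asymmetry is in the text, and its direction is certain where it applies. For any participant with an ALQ baseline and a falling titre, the within-arm percent reduction is understated in both the arithmetic and the log-ratio version. Quantifiable participants below 20 RU/ml dilute the pooled mean only if their signal falls less than true antibody.

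A reader might infer three stronger things that the documents do not support.

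- That the drug's autoantibody reduction will be understated overall. This depends on assay limits, ALQ frequency and dilution practice, none of which is given.
- That dropping BLQ baselines contributes to the understatement. It raises the mean reduction.
- That 14% of the anti-Dsg-3 table will be PF participants without target antibody. That is a ceiling, since negatives with a BLQ baseline are dropped.

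Nor can the contrast with placebo be called understated, because both arms follow the same rule. All magnitudes rest on the assumed 65% and 20% falls and the assumed distances above the limit. This is a cheap improvement to a descriptive endpoint and does not threaten the trial's conclusions.

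**What to change.** Keep Tables 14.2.3.3 and 14.2.3.4 as planned. In SAP 4.3.2, add for each antibody a companion summary of change and percent change, restricted to participants whose baseline for that antibody is quantifiable (neither BLQ nor ALQ) and at least 20 RU/ml. Show ALQ-baseline participants separately, or use a diluted re-assay value where the laboratory has one. Report the number of BLQ and ALQ values by arm and visit, so that a reader can judge how much the main tables are affected. Use one term for the limit in 2.3.3 and 4.3.2.

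The cost is SAP wording and one extra descriptive table. The serostatus cut already exists and no new data are needed. The companion table will have fewer participants and will leave out the highest titres, which is why it should sit beside the planned tables and not replace them.

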4.4 IMMUNOGENICITY

4.4.1 *Available data*

Blood samples will be collected for the determination of anti-drug antibodies (ADA) to efgartigimod (in serum samples) and antibodies against rHuPH20 (in plasma samples) at the time points indicated in the schedule of assessments (see section 9.5).

Immunogenicity samples are analyzed in a 3-tiered approach:

- All samples are evaluated in the ADA screening assay and are scored as ADA screening positive or negative.
- If a sample scored positive in the ADA screening assay, it is further evaluated in the confirmatory assay and is scored confirmed positive (positive immunodepletion) or confirmed negative (negative immunodepletion).
- If a sample is scored as confirmed positive, the samples are further characterized in the ADA titration assay (to determine titer) and are also further analyzed in the Nab assay to confirm neutralizing activity. For Nab against efgartigimod, a screening assay is performed and results will be reported as negative or positive. For Nab against rHuPH20, the screening Nab assay is followed by a titer Nab assay in case the sample screened positive.

[figure not shown]
If available, a titer result will be reported for the ADA confirmed positive samples. However, a titer result is not always available:

- In case the ADA confirmed positive sample could not be run in the titration assay (e.g., due to insufficient sample volume/quality to perform the titer analysis), the result will be described as ‘positive immuno-depletion’ and the sample should be considered as ADA positive.
- If a sample is negative in the titration assay, it will be reported as ‘negative titer’ but it should be considered as ADA positive since it was confirmed positive in the second tier.
- If a sample could not be analyzed or reported as ‘positive screen’, the ADA sample status is ADA unevaluable.

An overview of this 3-tiered approach and all possible ADA sample results that will be reported by the laboratory is given below. From these reported ADA sample

results a final ADA sample status needs to be derived during the statistical analysis, as presented in the final column ('Final ADA Outcome'):

Figure 1: ADA sample status

^a missing screen includes the following terms (reported as reason not done): NA (not analyzed), NR (no result), NS (no sample) and SL (sample lost). More details can be found in the IS data transfer agreement (DTA) from LGC (for ADA against efgartigimod) and the DTA from Covance Indianapolis (for antibodies against rHuPH20) with SGS SDO.

^b 'positive titer' is reported in case it was not possible to retrieve a numeric value.

4.4.2 Derivation rules

4.4.2.1 PARTICIPANT CLASSIFICATION FOR ADA AGAINST EFGARTIGIMOD

Table 6 below gives an overview of how the ADA participant classification will be derived, starting from the participant baseline ADA sample status.

Table 6: Participant classification for ADA against Efgartigimod

Participant ADA classification	Highest ^c post-baseline sample status				
	ADA negative	ADA positive (missing titer ^a)	ADA positive (negative titer ^b or numeric titer value)		ADA not evaluable
Baseline ADA sample status					
ADA negative	ADA negative	Treatment-Induced ADA	Treatment-Induced ADA		ADA unevaluable
ADA positive (missing titer^a)	Treatment-Unaffected ADA	ADA unevaluable	ADA unevaluable		ADA unevaluable
ADA positive (negative titer^b or numeric titer value)	Treatment-Unaffected ADA	ADA unevaluable	titer < 4 x baseline titer: Treatment-Unaffected ADA	titer ≥ 4x baseline titer: Treatment-Boosted ADA	ADA unevaluable
ADA not evaluable	ADA unevaluable	ADA unevaluable	ADA unevaluable		ADA unevaluable

^a Samples with missing titer have as reported ADA result 'positive immunodepletion' or 'positive titer';

^b Results reported as 'negative titer', i.e. titer value <1 will be set to value of 1;

^c Highest sample status, with order: (from low to high): ADA unevaluable, ADA negative, ADA positive (missing titer /positive immunodepletion), ADA positive with titer ≤ 1 ('negative titer' as reported ADA result, titer value set to 1), ADA positive with titer >1 (i.e. positive titer and selecting the sample with highest titer)

ADA evaluable participant = participant classified as any of following categories: ADA negative, treatment-unaffected ADA, treatment-induced ADA, treatment-boosted ADA. The first 2 categories are classified as 'ADA negative', the latter 2 as 'ADA positive'.

ADA unevaluable participant = participant classified as ADA unevaluable or with missing baseline ADA sample or without post-baseline ADA samples.

Note: Fourfold difference in titer values is considered significant in case a twofold serial dilution is applied (= 2 times the dilution factor) (reference to Shankar et al., 2014).

ADA incidence = percentage of participants with treatment-induced or treatment-boosted ADAs (denominator: number of evaluable participants).

ADA prevalence = percentage of participants with treatment-unaffected ADA, treatment-induced ADA or treatment-boosted ADA (denominator: number of evaluable participants).

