
 To evaluate the PD of efgartigimod PH20 SC in participants with PV or PF 	
 Total IgG and subtype (IgG1, IgG2, IgG3, IgG4) serum levels Anti-Dsg-1 and -3 autoantibodies serum levels

 To evaluate the immunogenicity of efgartigimod PH20 SC in participants with PV or PF 	
 Incidence and prevalence of anti-drug antibodies (ADAs) against efgartigimod and antibodies against recombinant human hyaluronidase (rHuPH20)

 To evaluate the competency of participants or caregivers to self-administer efgartigimod PH20 SC 	
 Number and percentage of participants or caregivers completing the self-administration training Number and percentage of participants or caregivers determined by the site staff to be sufficiently competent to self-administer efgartigimod PH20 SC Number and percentage of participants or caregivers that self-administer efgartigimod PH20 SC under site staff supervision
Exploratory	

 To evaluate the disease-specific genetic background and effects of efgartigimod PH20 SC on the serological and immunological profiles of participants with PV or PF 	
 Anti-Dsg-1 and -3 autoantibody subtypes and autoantibody reactivity to Dsg domains and other antigens Lymphocyte dynamic changes Serum cytokines profiles DNA and RNA genetic profiles

 To evaluate the effects of efgartigimod PH20 SC on markers of pemphigus pathology in skin of participants with PV or PF 	
 Markers of pemphigus pathology in lesional and non-lesional skin

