Anti-rHuPH20 Ab incidence = percentage of participants with treatment-induced or treatment-boosted rHuPH20 Ab s (denominator: number of evaluable participants).

Anti-rHuPH20 Ab prevalence = percentage of participants with treatment-unaffected rHuPH20 Ab, treatment-induced rHuPH20 Ab or treatment-boosted rHuPH20 Ab (denominator: number of evaluable participants).

	Statistical Analysis Plan	
ARGX-113-1904	Final analysis	Final 2.0 of 22NOV2023

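### ADA, anti-rHuPH20 antibody and rHuPH20 NAb prevalence drops participants positive both at baseline and afterwards when only a deciding titre is missing, which can only lower the figure

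*SAP*

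**What the plan says.** Protocol Section 3 lists as a secondary endpoint "Incidence and prevalence of anti-drug antibodies (ADAs) against efgartigimod", together with the same measures for antibodies against rHuPH20.

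SAP 4.4.1 covers a confirmed-positive ADA sample that could not be run in the titration assay: "the sample should be considered as ADA positive".

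SAP 4.4.2.1 classifies each participant by crossing the baseline sample status with the highest post-baseline status (Table 6). It then defines "ADA prevalence = percentage of participants with treatment-unaffected ADA, treatment-induced ADA or treatment-boosted ADA (denominator: number of evaluable participants"). Those outside the denominator are given by "ADA unevaluable participant = participant classified as ADA unevaluable or with missing baseline ADA sample or without post-baseline ADA samples".

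SAP 4.4.2.2 repeats the construction for rHuPH20: "Anti-rHuPH20 Ab prevalence = percentage of participants with treatment-unaffected rHuPH20 Ab, treatment-induced rHuPH20 Ab or treatment-boosted rHuPH20 Ab (denominator: number of evaluable participants"). Table 7 has the same cells as Table 6. Section 4.4.2.4 and Table 9 do likewise for neutralizing antibodies against rHuPH20. Table 8, for neutralizing antibodies against efgartigimod, uses no titre.

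**The concern.** Incidence needs the titre. In a participant who was already positive at baseline, only a fourfold rise tells boosted from unaffected, so without both titres the participant cannot be placed. Prevalence does not need that distinction, because unaffected and boosted are both in its numerator. Using the incidence denominator for prevalence therefore discards participants whose prevalence status is fully known.

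The rule is also uneven within one row of Table 6. A participant with an untitred positive baseline sample and negative post-baseline samples is treatment-unaffected and counts as prevalent. With the same baseline and a positive post-baseline sample, the participant is dropped. The one with more evidence of antibodies is the one left out.

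At stake is the accuracy of a named, descriptive secondary endpoint. Placebo also contains rHuPH20, so the rHuPH20 figures are affected in both arms.

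**Working it through.** **Step 1: enumerate Table 6** (Table 7 is identical; Table 9 has the same pattern). Results reported as a negative titre are given a fixed value by the SAP, so they count as titred.

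| Baseline | Post: negative | Post: positive, no titre | Post: positive, titred | Post: not evaluable |
|---|---|---|---|---|
| Negative | negative | induced | induced | unevaluable |
| Positive, no titre | unaffected | **unevaluable** | **unevaluable** | unevaluable |
| Positive, titred | unaffected | **unevaluable** | unaffected or boosted | unevaluable |
| Not evaluable | unevaluable | unevaluable | unevaluable | unevaluable |

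Unevaluable cells: 1 + 3 + 2 + 4 = 10 of 16. Of these, 3 + 2 + 2 = 7 contain a positive sample. In three of the seven (bold) both sides are known and only a titre is missing. In the other four, one side is not evaluable.

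**Step 2: direction for the three bold cells.** They contain positives only. Let N be the participants with both sides evaluable, x the positives among them, and k the number in the bold cells. The SAP reports (x − k)/(N − k). This is below x/N whenever k > 0 and x < N.

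**Step 3: size.** The plan states no figure to reproduce. N = 142 is two thirds of the planned 213, taking everyone as having both sides evaluable; x and k are assumptions.

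- x = 28: 28/142 = 19.7%. k = 1, 3, 5 gives 27/141 = 19.1%, 25/139 = 18.0%, 23/137 = 16.8%.
- x = 14: 14/142 = 9.9%. k = 1, 3, 5 gives 13/141 = 9.2%, 11/139 = 7.9%, 9/137 = 6.6%.

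k cannot exceed the number who are positive at baseline and still positive afterwards. If 5% are positive at baseline and 30% of those turn negative (both assumed), that number is 142 × 0.05 × 0.70 ≈ 5. On those assumptions k = 5 means that every such participant lacks a deciding titre, so it is an upper limit.

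**Step 4: the four cells with one side missing.** Assume 5% positive at baseline, 15% of the rest induced, 30% of baseline positives turning negative, and each side missing in 10% independently of antibody status.

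- True prevalence: 0.05 + 0.95 × 0.15 = 19.25%. Post-baseline positive: 0.05 × 0.70 + 0.95 × 0.15 = 17.75%.
- SAP rule: only the 81% with both sides are used, and independence leaves their prevalence at 19.25%. A simulation of 2,000,000 participants agreed (19.3% against 19.3%).
- Denominator of anyone with at least one evaluable side: (0.81 × 0.1925 + 0.09 × 0.05 + 0.09 × 0.1775)/0.99 = 0.1764/0.99 = 17.8%.
- Adding back only the known positives: 0.1764/(0.81 + 0.0045 + 0.015975) = 21.2%.

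Under independent missingness the SAP rule is right for these cells, and both simple replacements are wrong.

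**The case against.** A reader might infer that all seven positive-containing cells pull prevalence down. The documents do not support that. For the four cells with one side not evaluable, Table 6 also drops the matching participants with one negative side, so negatives leave as well. Step 4 shows no bias when missingness is unrelated to antibody status. A downward bias would need positives to be more likely to lose a sample, and nothing in the documents says so.

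It may also be said that Table 6 does not contradict 4.4.1, which is a rule about samples. That is fair. The table labels untitred samples as positive, and a baseline-negative participant with an untitred positive sample afterwards counts as treatment-induced. A missing titre never removes a baseline-negative participant. The inconsistency arises only when the participant class is carried into prevalence.

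The reach is limited further by footnote c to Table 6, which ranks titred positive samples above untitred ones. A missing post-baseline titre matters only if no positive post-baseline sample has a titre, and sampling is repeated (every 2 weeks to week 9, then every 4 weeks). A missing baseline titre has no such safeguard.

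Finally, the loss is not hidden. SAP 4.4.3 tabulates unevaluable participants and baseline sample status, and lists all sample results and classifications. The endpoint is summarized descriptively (Protocol 9.5.8) and lies outside the testing sequence in SAP 4.1.4. This limits the harm, but the reported prevalence would still be the uncorrected one.

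**Conclusion.** The point holds for three cells in each of Tables 6, 7 and 9 (baseline/post-baseline titre missing/missing, missing/present, present/missing). There the participant is positive on both sides, and removal can only lower ADA, anti-rHuPH20 antibody and rHuPH20 NAb prevalence. The direction follows from the definitions alone. The size does not: the documents give no prevalence or missing-titre rate, and SAP 4.4.1 only names insufficient sample volume or quality as a reason for a missing titre. The illustration runs from 0.6 points (19.7% to 19.1%, one participant lost) to 2.9 points (19.7% to 16.8%, five lost), the latter being the limit under the baseline-positive rate assumed above. This is a minor correction to a descriptive endpoint. It does not extend to participants with one side missing, nor to Table 8, where titre plays no part. Incidence is correctly defined as it stands.

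**What to change.** Leave the classification tables and the incidence definitions as they are. In SAP 4.4.2.1, 4.4.2.2 and 4.4.2.4, redefine prevalence: among participants whose baseline and post-baseline status are both evaluable, the percentage with at least one positive sample, whatever the titre. Positive means confirmed positive for ADA and rHuPH20 antibodies, and NAb positive for rHuPH20 NAb, where no confirmatory tier is planned in the main analysis.

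Show the prevalence denominator next to the incidence denominator in Tables 14.2.4.1.2, 14.2.4.1.6 and 14.2.4.1.8. The difference between the two is the number of participants rescued.

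Do not widen the main denominator to anyone with at least one evaluable sample, and do not add back only the known positives. If participants with one side missing are of interest, give them a sensitivity analysis with a stated denominator. Leave 4.4.2.3 unchanged on this point.

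The cost is one sentence in each of three sections and one extra denominator in three tables. No new data are needed.
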